# **Procedure**

On Day 1 of the study, all patients will undergo clinical assessments to measure change in reading speed (MNREAD). Near refraction will be measured and, based on this, a pair of single vision spectacles will be made for each subject for testing purposes. On Day 2, all patients will return to the clinic for baseline assessments detailed instructions on running the PAECT platform and training on Module 1 of the platform. For those patients assigned to the clinical arm of the study, appointments will be made to

return at weekly intervals for two-hour PAECT training sessions. During these sessions, the subjects will run the PAECT program in the clinic, with feedback and encouragement given by the therapist.

There will be a total of *eight training sessions*. For those patients assigned to the At-home arm, arrangements will be made to deliver and set up a computer in their home. These subjects will be instructed to practice with the PAECT program as often as possible, but at least two hours per week. Patients will receive weekly from calls from the Program Coordinator, who will answer technical questions and encourage frequent use of the program, but no feedback about performance will be given. All patients in both arms will return to the clinic after one month, and two months to undergo assessments of reading performance. Each subject will participate in the study for 12 weeks: 1 screening visit, 1 baseline testing visit, 4 weeks of training, Month 1 assessment visit, 4 weeks of additional training, and a final assessment visit.

### **Patient Recruitment**

Veteran patients will be recruited from the eye clinics of the Jesse Brown VAMC, Veteran and Non-Veteran patients from the University of Illinois at Chicago (UIC) Department of Ophthalmology and Visual Sciences, and Captain James A. Lovell Federal Health Care Center in North Chicago. We have ongoing collaborations with these sites and have successfully recruited from these centers for past studies. All potential patients will undergo a standard clinical examination at the recruitment sites to determine eligibility for the study.

Both Veterans and Non-Veterans will be recruited for this study, with priority given to eligible Veterans. The strict inclusion criteria will require additional subjects (non-veterans) to also be included in recruitment. This will allow us to meet recruitment levels specified by our VA Merit Review Grant. Non-veterans will not have medical records at the VA but their data will be stored and protected in an approved off-site VA laboratory. All data will be stored in a locked cabinet in a locked room with only research personnel access.

# **Inclusion Criteria**

Patients with a diagnosis of retinal disease affecting the central visual field (e.g., non-exudative "dry" AMD) and a central scotoma, with visual acuity of less than or equal to 20/70 and greater than or equal to 20/400 (in the test eye) will be included in the study. The presence of a central scotoma and eccentric viewing will be confirmed using an Opko OCT/SLO Microperimeter. Our intent is to include subjects based upon their functional characteristics (e.g., eccentric viewing).

### **Exclusion Criteria**

Patients will be screened to exclude those with other major ophthalmologic or neurologic disease, choroidal neovascularization ("wet" AMD), moderate to severe media opacities, and cognitive impairment. Patients' disease status will be monitored throughout the study.

# **Research Design and Statistical Analysis Plan**

We will recruit eligible patients per year for each of the three years for Phase 2 of the study to be assigned randomly to the Laboratory Group, while others will be assigned to an At-home Training Group. Three assessments will be taken for each subject: at

baseline, and after 1 and 2 months. To analyze the assessment data, we will utilize a two-way (group by time) repeated measures design. A major advantage of this design is subject homogeneity; that is, subject effects are reduced.

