### **Methods of Procedure:**

Our previous laboratory studies have demonstrated that eye movement control training significantly improves reading performance. In the proposed study, we will translate our methods into clinical practice with a large sample of patients with central vision loss.

In Phase 1, we will develop a standardized, user-friendly, computer-based platform that will allow patients to easily self-administer training exercises. The software platform will be designed to automatically choose the appropriate exercises based on a patient's previous performance, run the training exercise, and collect performance data into a universal patient data file. In Phase 2, the platform will be tested in two settings: in standard clinical rehabilitation practice and in the patient's home. Reading outcomes in the two settings will be compared.

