# Phase 2 - Clinic-Based Versus Home-Based Training

In this phase, we will compare reading outcomes from training with PAECT in a low-vision clinic setting and with feedback on performance given by a rehabilitation therapist to training with the PAECT by the patients in their own homes. We have previously demonstrated in our laboratory experiments that eye movement training exercises increase reading speed, but we wish to know whether these findings can be extrapolated to clinical practice. The results of this study will allow us to quantify the role of direct support and feedback from the therapist during each session versus any advantages that may result from more frequent practice on the exercises afforded by having the equipment at home.

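### Entry acuity, known at screening and spanning 20/70 to 20/400, is used neither to allocate nor to analyse, and the plan does not say that allocation is opened only after the baseline test

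*Combined protocol and SAP*

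**What the plan says.** The allocation rule is one clause in the section Research Design and Statistical Analysis Plan: patients are to be "assigned randomly to the Laboratory Group, while others will be assigned to an At-home Training Group". No section adds a ratio, a way of generating the sequence, concealment, blocks, strata or minimisation. The same section plans a two-way, group-by-time repeated measures analysis of three assessments (baseline, one month, two months) and names no covariate.

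Inclusion Criteria admits patients with "visual acuity of less than or equal to 20/70 and greater than or equal to 20/400" in the test eye and any retinal disease affecting the central field, with dry AMD as an example. Patient Recruitment lists three centres and states: "Both Veterans and Non-Veterans will be recruited for this study, with priority given to eligible Veterans".

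Procedure gives MNREAD testing on Day 1 and baseline assessments for all patients on Day 2. It then goes on to patients who have been assigned to an arm. It does not say when the assignment is made or revealed.

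The number of patients cannot be read in the public text ("We will recruit eligible patients per year for each of the three years for Phase 2"). The only description of size is in Methods of Procedure: "with a large sample of patients with central vision loss".

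**The concern.** Acuity is a natural candidate for a factor that governs how much a patient with central vision loss gains from eye movement training. It is measured at eligibility, so using it costs nothing in data collection. If the arms differ in acuity by chance, and acuity affects the gain in reading speed, the home-versus-clinic contrast in that trial carries part of the acuity difference. The main question is whether home training is as effective as clinic training, so an imbalance that hides a difference does as much harm as one that creates it. Leaving acuity out of the model also leaves explainable variation in the error term.

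Timing is a separate route. The baseline reading test depends on effort, and baseline is one level of the group-by-time contrast. If a patient or tester knows the arm beforehand, any effect of that knowledge on the baseline score passes straight into the estimated change.

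**Working it through.** The plan states no sample size, power, alpha or effect size, so there is no figure of its own to reproduce.

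**Inputs**
- Acuity limits, from Inclusion Criteria: log10(70/20) = 0.544 and log10(400/20) = 1.301 logMAR, a span of 0.757.
- Assumed: acuity uniform on logMAR, so SD = 0.757/√12 = 0.219.
- Assumed: simple 1:1 allocation. The documents give neither method nor ratio.
- Assumed: total N from 30 to 200.

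**Chance of an acuity gap of at least 0.10 logMAR.** The SE of the difference in arm means is 0.219 × √(2/n) with n per arm, and the probability is 2 × [1 − Φ(0.10/SE)]. The simulation tosses a coin for each patient, so arm sizes vary. Repeat runs differ by about a point.

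| Total N | SE (logMAR) | Normal approximation | Simulation, simple allocation | Simulation, stratified blocks |
|---|---|---|---|---|
| 30 | 0.080 | 21% | 22% | 3% |
| 40 | 0.069 | 15% | 15–16% | 1% |
| 60 | 0.056 | 8% | 8% | 0.1% |
| 100 | 0.044 | 2% | 2–3% | 0% |
| 200 | 0.031 | 0.1% | 0.1% | not run |

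**What such a gap does to the contrast.** A gap of 0.10 logMAR is 0.10/0.219 = 0.46 SD of acuity. If acuity correlates r with change in reading speed, the contrast shifts by r × 0.46 SD of change. That is 0.14 SD at r = 0.3 and 0.23 SD at r = 0.5. These correlations are assumptions.

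**Error rates with no true difference** (8,000 simulated trials per setting, r from 0.3 to 0.7, analysis without acuity). Averaged over all trials, type I error is about 5%. Among trials with an acuity gap above 0.5 SD it is 7–20% at 15 per arm, where such gaps occur in about 17% of trials. It is 9–32% at 30 per arm, where they occur in about 5%. With acuity in the model it is 4–6% in the same trials. If allocation is stratified but acuity is left out of the model, the test becomes conservative, at 0.015–0.033 for r of 0.5 and 0.7.

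**Precision.** Adjustment multiplies the SE by √(1 − r²), less a small cost for estimating the slope, roughly a factor √(1 + 1/(N − 4)).
- r = 0.3: √0.91 = 0.954. With the slope cost at N = 30 this is 0.954 × 1.019 = 0.972, a cut of about 3%. It approaches 5% in large trials.
- r = 0.5: √0.75 = 0.866, a cut of up to about 13%.
- r = 0: a loss of about 1% (for example √(1 + 1/56) = 1.009 at N = 60).

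For scale, take an assumed 0.5 SD effect, 80% power and two-sided 0.05. The unadjusted requirement is 63 per arm. It falls to 58 at r = 0.3 and 48 at r = 0.5.

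**Form of the model term.** In complete repeated-measures data, a main effect of acuity shifts all of a patient's assessments equally and cancels from the group-by-time contrast. To matter, acuity must enter as acuity by time, or as a covariate in a model of follow-up reading speed adjusted for baseline.

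**The case against.** The strongest reply is that simple randomisation is valid. Chance imbalance is part of the sampling error that the test already allows for, and the raised error rates above apply only after conditioning on a bad draw. That stands: there is no systematic bias here. It also stands that the group-by-time contrast uses each patient's own baseline, so stable differences in reading speed due to acuity, diagnosis or source drop out. Only factors that change the response to training remain, and no section shows that acuity is one. With N out of sight and the sample called large, the imbalance risk may be negligible.

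Four stronger readings are tempting, and the documents do not support them.
- A reader might infer that the plan chose simple randomisation. It is silent on method, so the percentages show what follows if assignment is simple.
- A reader might infer that only the first group is randomised, because of "while others will be assigned to an At-home Training Group". The sentence has evidently lost its patient counts, and the natural reading is one random assignment to two groups.
- A reader might take unequal arm sizes as a threat. A 60:40 split keeps 4 × 0.6 × 0.4 = 96% of the information of 1:1 and cannot pass for a treatment difference.
- A reader might think that the name Laboratory Group changes the comparator. The Phase 2 section places that training "in a low-vision clinic setting and with feedback on performance given by a rehabilitation therapist", so the label is a clerical slip.

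On timing, Procedure does list the Day 2 baseline assessments before it mentions arms. That order of narration suggests, but does not require, that the arm is unknown at baseline.

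**Conclusion.** The point holds as an inexpensive improvement, not as a flaw that invalidates the trial. Entry acuity is known, varies widely and is unused. Using it would improve precision and limit chance imbalance in a factor that may affect response. The size depends on two things that the documents do not give: N, and the link between acuity and training gain. Below about 50 per arm the imbalance risk is worth removing; at 100 per arm it is about 0.1% for a 0.10 logMAR gap. The gain in precision depends on the assumed correlation far more than on N.

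The timing gap does not depend on N. If the arm can be known before baseline, there is a route to real bias, though nothing in the documents shows that it would be used, and its size cannot be estimated.

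**What to change.** 1. State that patients are allocated 1:1 from a concealed, computer-generated list, stratified by entry acuity band, in permuted blocks of randomly varying size larger than 2 (for example 4 and 6). Training is open, so past assignments are visible; with blocks of 2 and 4, guessing the arm that is behind is right about 72% of the time, against 50% under simple allocation. Larger blocks reduce this but do not remove it. Add recruitment source as a stratum only if N allows.
2. State that the allocation is opened only after the Day 2 baseline assessments are complete, including the MNREAD that serves as baseline.
3. Put entry acuity in the analysis as an acuity-by-time term, or as a covariate in a model of follow-up reading speed adjusted for baseline. Do not rely on a main effect alone.

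The cost is a few sentences in the protocol and SAP, a new list, a few strata to administer, one or two model degrees of freedom (about 1% in standard error if acuity proves irrelevant) and some remaining predictability of assignments. No extra visits, measurements or patients are needed.

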## **Key Questions:**

The key question of this proposed research project is whether a series of eye movement training exercises that we have validated in our laboratory environment can be translated into a home-based training system.

The primary question that this research is designed to answer is: Can a home-based eye movement training program be as effective as a clinically administered program? In order to answer this question, we will assess whether the opportunity for increased practice afforded by having the program available at home results in improved reading performance.

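### The group-by-time analysis names no home-minus-clinic contrast or confidence interval, so nothing in the plan yet estimates the difference that the as-effective question turns on

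*Combined protocol and SAP*

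**What the plan says.** Key Questions poses the primary question: "Can a home-based eye movement training program be as effective as a clinically administered program". The next sentence is worded as superiority: "we will assess whether the opportunity for increased practice afforded by having the program available at home results in improved reading performance". Methods of Procedure adds only "Reading outcomes in the two settings will be compared".

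Research Design and Statistical Analysis Plan lists three assessments, "baseline, and after 1 and 2 months", and then gives the whole analysis: "To analyze the assessment data, we will utilize a two-way (group by time) repeated measures design". The only reason offered is that subject effects are reduced. The Procedure section describes the MNREAD assessments as measuring change in reading speed and ends the schedule with "4 weeks of additional training, and a final assessment visit".

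No section says which model term answers the question. None gives a primary time point, a confidence interval, a baseline covariate or a margin.

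**The concern.** The question has a direction: how much worse, if at all, is home than clinic? A two-way repeated measures design with three visits offers several candidate answers: the group main effect, the 2-df interaction, and a change contrast at either follow-up visit. They do not estimate the same thing.

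- The interaction F statistic has the same distribution whether home is better or worse by a given amount.
- The group main effect averages in baseline, where randomised groups are expected to be equal, so it dilutes the Month 2 difference.
- With no contrast named, the choice can be made after results are seen, and a non-significant interaction could be reported as showing that home is as effective.

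A reader judging the primary question needs the home-minus-clinic difference and its interval, because the limit on the side unfavourable to home shows how large a deficit the data still allow.

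A secondary matter is efficiency. With baseline only as a level of time, the natural contrast is a change from baseline, which usually has a somewhat wider interval than one that uses baseline as a covariate.

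**Working it through.** **Inputs.** The documents state no effect size, SD, correlation, alpha or margin, and the available text shows no sample size (a number may have been lost from it, which is not counted as an error). There is therefore no figure of the plan's own to reproduce. Everything below is illustrative. It assumes both arms randomised 1:1, n = 30 per arm, two-sided 5%, unit SD at every visit, and the same correlation r between any two visits. The true home deficit at Month 2 is 0.5 SD. By visit, the deficit is either (0, 0.25, 0.5), building up, or (0, 0.5, 0.5), full at Month 1.

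**1. Interaction test.** Noncentral F with 2 and 2(2n − 2) = 116 df and noncentrality λ = (n/2) × Σ(d_t − mean d)² / (1 − r).

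- Building up: Σ = 0.125. At r = 0.7, λ = 15 × 0.125/0.3 = 6.25 and power is 0.591.
- Full at Month 1: Σ = 0.1667. At r = 0.7, λ = 15 × 0.1667/0.3 = 8.33 and power is 0.724.

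Reversing the sign of every d_t leaves λ unchanged, so the test cannot tell home better from home worse.

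**2. Baseline-adjusted Month 2 difference.** SE = √[2(1 − r²)/n × (1 + 1/(2n − 4))] on 2n − 3 = 57 df. The last factor allows for chance baseline imbalance. At r = 0.7, SE = 0.186 and power is 0.752.

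**3. Probability of non-significance when home is truly 0.5 SD worse at Month 2.**

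| r | Interaction, building up | Interaction, full at Month 1 | Adjusted Month 2 |
|---|---|---|---|
| 0.6 | 53% | 41% | 34% |
| 0.7 | 41% | 28% | 25% |
| 0.8 | 22% | 11% | 12% |

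Both tests miss the deficit often enough that non-significance of neither supports equivalence.

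**4. Group main effect.** It estimates the mean of d over the three visits: 0.25 (building up) or 0.333 (full at Month 1), that is 1/2 or 2/3 of the Month 2 difference. Simulated power at 30 per arm and r = 0.7 was 0.19 and 0.29.

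**5. Precision.** The Month 2 change contrast has SE √[4(1 − r)/n]. Under the assumed covariance the planned design can pool its error on 2(2n − 2) df; a stand-alone change score has 2n − 2 df. At r = 0.7 the 95% half-widths are 0.373 SD (adjusted), 0.396 (pooled) and 0.400 (stand-alone). Width ratios at 30 per arm:

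| r | Adjusted / pooled | Adjusted / stand-alone |
|---|---|---|
| 0.5 | 0.883 | 0.874 |
| 0.6 | 0.912 | 0.903 |
| 0.7 | 0.940 | 0.930 |
| 0.8 | 0.968 | 0.957 |
| 0.9 | 0.994 | 0.984 |

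Against pooled error at r = 0.9, the ratio is 1.005 at 20 per arm and 1.045 at 10 per arm: no gain, and then a small loss.

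**6. Which follow-up contrast.** The adjusted mean of Months 1 and 2 has per-patient variance (1 + r)/2 − r², which is 0.36 at r = 0.7. Its power is 0.882 if the effect is full at Month 1 and 0.655 if it builds up, against 0.752 for Month 2 alone in both cases.

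**The case against.** The strongest reply is that the planned design is valid and already contains what is needed. A group-by-time model yields a signed home-minus-clinic change contrast with an interval, change from baseline matches how the Procedure section describes the outcome, and nothing in the plan rules out a covariate. All of that stands. A reader might infer that repeated measures is the wrong method here; the documents do not support that. The gap is that no contrast is chosen.

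A reader might also infer that the plan intends to treat a non-significant interaction as proof that home is as effective. It nowhere says so. The risk arises because the deciding term and the rule for interpreting it are left open.

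The efficiency argument is limited too. The fair comparator is the pooled repeated-measures error, which shrinks the gain. The size depends on N and r, which the documents do not give, and on equal SDs, which are assumed. The covariate does not itself prevent misreading: the adjusted test has its own miss rate, and at r = 0.8 with the effect full at Month 1 the interaction misses slightly less often (11% against 12%).

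Finally, Month 2 is not declared primary anywhere, and Key Questions also carries a superiority wording. Both are fair limits on how far a reviewer should dictate the contrast.

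**Conclusion.** The point holds. The plan commits to no between-arm estimate for its primary question, and the test most often taken from such a design is non-directional. With the assumed 30 per arm, it would be non-significant in 11% to 53% of trials despite a true 0.5 SD home deficit at Month 2.

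Using baseline as a covariate is a worthwhile but modest improvement, not a correction of an invalid analysis. Nor would a baseline-adjusted interval by itself settle the question, though a reader might infer that it would. It shows which differences remain compatible with the data; without a margin it cannot establish that home is as effective.

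The absence of a named contrast and interval is read directly from the text. All the magnitudes rest on the assumed sample size, correlation, equal SDs and effect pattern. This is a change that should be made; its main value is a stated, directional estimate.

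**What to change.** Before any outcome is compared by arm, add the following to the analysis plan:

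- **Model.** Month 1 and Month 2 MNREAD reading speed with arm, visit, arm-by-visit and baseline reading speed as a covariate. A longitudinal model with baseline means constrained equal gives about the same precision and is an acceptable alternative.
- **Primary contrast.** Name one home-minus-clinic difference. Month 2, the final assessment, is a natural candidate, but the investigators should choose between it and the mean of Months 1 and 2 according to when they expect the effect to appear.
- **Reporting.** Give that difference with its 95% CI and keep the interaction as supportive.
- **Interpretation.** State that non-significance of any test will not be read as showing that home is as effective. That conclusion needs a margin justified clinically by the investigators; no value is proposed here.

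The cost is wording only: no added visits, patients or measurements. Statistically it takes about one degree of freedom, with a slightly wider interval possible in a small trial with high correlation. Choosing Month 2 alone gives up about 13 points of power against the two-visit mean if the effect is full by Month 1 (75% against 88% at r = 0.7) and gains about 10 if it builds up (75% against 66%, from 0.752 and 0.655 before rounding).
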